Following completion of the screening and baseline evaluations, subjects included in the Phase Ia, Arm B part of the trial will receive treatment with M3814 at a starting dose of 50 mg QD for 7 consecutive weeks. During this period, RT (2 Gy x 33 to 35, 5 F/W) is given with concurrent cisplatin administration. The administration of M3814 will take place 1.5 hours (\pm 30 minutes) before the start of RT. This arm will be initiated after the first dose level (100 mg) in Arm A has been completed and evaluated by the SMC.

The dose escalation in Arm B will commence with the capsule formulation. Based on the findings in the tablet testing cohorts from Arm A, the SMC may decide to introduce the tablet formulation in Arm B. Subjects will only receive one formulation during their treatment.

In both arms, dose escalation will continue from the starting dose of M3814 up to a maximum dose of M3814 800 mg/day until one of the following stopping rules apply: a maximum number of 30 subjects are included, more than three cohorts are assigned to the same dose level or the estimate for DLT probability of the MTD reaches sufficient precision. It is anticipated that up to 30 evaluable subjects (10 cohorts of 3 subjects) may be needed in each arm in order to determine the MTD of M3814 (see Section 8 for details).

Phase Ib

Following completion of the screening and baseline evaluations (see Section 5.3 for entry criteria), subjects enrolled in the Phase Ib part of the trial (expansion cohort for Arm A - NSCLC) will receive M3814 QD at one dose level below the RP2D, to be given 1.5 hours (\pm 30 minutes) before each RT (2 Gy) fraction for up to 33 fractions. The first 3 NSCLC subjects included in the Phase Ib (Arm A) part will be treated with M3814 one dose level below the RP2D to evaluate the safety of M3814 when given to subjects in the curative setting. Based on the safety profile seen in the first 3 subjects, the SMC will decide if the dose of M3814 can be escalated to the RP2D. It is planned to enroll up to 27 evaluable subjects with Stage III A/B NSCLC in the Phase Ib (Arm A) part of the trial, and a further expansion cohort for Arm B (SCCHN) is planned to enroll up to 27 evaluable subjects with SCCHN, using the RP2D defined in Phase Ia, Arm B.

Ancillary cPoP part

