7.4.1.5 Dose Limiting Toxicities

A DLT is defined as any Grade ≥ 3 nonhematologic AE or any Grade ≥ 4 hematologic AE (according to NCI-CTCAE version 4.03) that is related to any of the study treatments and occurs during the DLT period of 5 weeks (Phase Ia, Arm A) or 12 weeks (Phase Ia, Arm B and Phase Ib, first 3 subjects in the expansion cohort of Arm A [NSCLC]) after the first dose of M3814.

A DLT must be confirmed by the SMC.

In addition, the following are considered DLTs:

1. Grade 3 thrombocytopenia with medically concerning bleeding

2. Febrile neutropenia
3. Any toxicity or study treatment-related TEAE that, in the opinion of the SMC, is of potential clinical significance such that further dose escalation would expose subjects to unacceptable risk
4. Any toxicity related to study treatments that causes the subject to receive less than 80% of the planned RT dose
5. Any toxicity related to study treatments leading to an interruption of RT longer than 1 week in Arm B
6. Evidence of study treatment-related hepatocellular injury for more than 3 days, such as > 5 -fold elevations above the ULN of ALT or AST (CTCAE Grade 3 or 4) with or without elevation of serum total bilirubin to $> 2 \times$ ULN, without initial findings of cholestasis (elevated serum alkaline phosphatase) or other apparent clinical causality.

The following study treatment-related AEs are exceptions to the above mentioned DLT definition and are **not** considered to be DLTs:

1. Mucositis (mucosal inflammation), including oral mucositis (stomatitis) of Grade ≥ 3 lasting for ≤ 4 weeks after completion of the study treatments
2. Stomatitis associated toxicities (e.g., swallowing dysfunction [odynophagia, dysphagia], decreased appetite or weight loss due to difficulty or painful swallowing) of Grade ≥ 3 lasting for ≤ 4 weeks after completion of the study treatments
3. Diarrhea of Grade ≥ 3 (≤ 3 days duration) following adequate and optimal therapy
4. Nausea and vomiting of Grade ≥ 3 (≤ 3 days duration) with adequate and optimal therapy
5. Radiation dermatitis and associated toxicities of Grade ≥ 3 lasting for ≤ 4 weeks after completion of the study treatments
6. Neutropenia of Grade 4 lasting for ≤ 5 days and not associated with fever
7. Isolated Grade 4 lymphocytopenia without clinical correlate
8. Fatigue or headache of Grade 3 (≤ 7 days duration) following initiation of adequate supportive care

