8.2 Definition of Analysis Sets and Subgroups

All Subjects Analysis Set (ALL):

The All subjects (ALL) analysis set will include all the subjects who have signed the ICFs (i.e., screening failures plus subjects enrolled).

Safety Analysis Set (SAF):

The Safety analysis set will include all subjects who receive at least one administration of the trial treatment (either M3814, RT or Cisplatin).

Full Analysis Set (FAS):

The Full Analysis Set will include all subjects who receive at least one administration of the trial treatment.

Dose Escalation Analysis Set (DE) :

The Dose Escalation (DE) analysis set will include all subjects treated in dose escalation cohorts who receive at least 80% of M3814 and RT planned dose and complete the DLT period (through 5 weeks [Phase Ia, Arm A] or 12 weeks [Phase Ia, Arm B] after start of M3814 treatment). The DE set will also include subjects treated in dose escalation cohorts who experience a DLT during the DLT period regardless of the received amount of each drug.

Pharmacokinetics Analysis Set (PK):

The PK evaluation (PK) analysis set in Phase Ia and Phase Ib parts will include subjects who have received at least the first dose of the drug and provided PK samples as per protocol for at least 6 hours following first dosing on Fraction Day 1.

Table 1: Summary of analyses and associated analysis set

Analyses	ALL	SAF	FAS	DE	PK
Disposition and deaths	✓				
Baseline Assessments		✓			
Past and Concomitant Therapies		✓			
Compliance and Exposure		✓			

CONFIDENTIAL
INFORMATION

12/60

Analyses	ALL	SAF	FAS	DE	PK
Primary endpoint: DLTs				✓	
Secondary efficacy endpoints			✓		
Safety and tolerability		✓			
Biomarker		✓			
Pharmacokinetics					✓

9

General Specifications for Data Analyses

Statistical analyses will be performed with SAS 9.4 or higher.

Pooling of centers:

Because of the anticipated small number of subjects enrolled in each center, data will be pooled across centers, and the factor center will not be considered in statistical models or for subgroup analyses.

Presentation of continuous and qualitative variables:

All outputs will be provided for each arm separately. No data between arms will be pooled, unless otherwise stated. For each arm, data will be presented by formulation, dose level and overall unless specified otherwise. The dose level will be defined by the planned dose of the corresponding cohort. If several cohorts have same dose level, there will be pooled together for all summary outputs.

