Mean, Min, Median, Max, GeoMean, 95% CI: 3 significant digits

SD: 4 significant digits

CV%, GeoCV%: 1 decimal place

Definition of baseline:

The last measurement prior to first administration of trial treatment (either M3814, RT or Cisplatin) will be used as the baseline measurement.

Definition of treatment day:

Treatment Day 1 is defined as the date of first administration of trial treatment (M3814 and/or RT and/or Cisplatin), the day before is defined as Treatment Day –1 (no Treatment Day 0 is defined).

Definition of on-treatment evaluations for safety analyses:

On-treatment evaluations for safety analyses will be evaluations performed on or after Treatment Day 1 until 30 days after the last dose of trial treatment or the clinical cut-off date (if the treatment is still ongoing).

Definition of duration:

Duration will be calculated by the difference of start and stop date + 1 (e.g. survival time (days) = date of death – date of first dose + 1), if not otherwise specified.

Conversion factors:

The following conversion factors will be used to convert days into months or years:
1 month = 30.4375 days, 1 year = 365.25 days.

Data handling after cut-off date:

Data after cut-off do not undergo the cleaning process. The only exceptions are the date of death and the date last known to be alive. Data obtained after the cut-off will not be displayed in any listings or used for summary statistics (e.g. laboratory values of samples taken after data cut-off, AE with onset date after data cut-off, etc.) will not be included in any analysis or listing.

For any adverse event or concomitant medication starting before the cut-off date, the end date will not be imputed (even if the end date is after the cut-off date) and will be presented as filled in the eCRF at the time of the data export.

Handling of missing data:

For identification of AE treatment emergence, incomplete dates will be handled as follows:

- In case the onset date is completely missing or the onset is in the same year (if the onset year is available only) or the onset is in the same month and year (if the day is missing) as start of trial treatment then the onset date will be replaced by the minimum of start trial treatment and AE resolution date.

- In all other cases, the missing onset day or onset month will be replaced by 1.

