- Incomplete stop dates will be replaced by the last day of the month (if day is missing only), if not resulting in a date later than the date of subject's death. In the latter case the date of death will be used to impute the incomplete stop date.
- In all other cases, the incomplete stop date will not be imputed.

In data listings, the documented date as given in the eCRF will be reported (e.g. __May2013 in case of day missing, but month and year available).

For identification of previous or concomitant medications/procedures, no formal imputation will be performed on missing or incomplete dates. Rules presented in [Table 3](#) will be used to define if a medication/procedure is considered as a previous, concomitant or both previous and concomitant medication/procedure.

Table 2: Stopping rules for medication/procedure end dates

End date of medication/procedure			Stopping rule
Day	Month	Year	
UNK	UNK	UNK	After treatment start (ongoing)
UNK	UNK	< Treatment start (year)	Before treatment start
UNK	UNK	>= Treatment start (year)	After treatment start
		< Treatment start (month and year)	Before treatment start
UNK		>= Treatment start (month and year)	After treatment start
		< Treatment start (complete date)	Before treatment start
		>= Treatment start (complete date)	After treatment start

UNK = Unknown

Table 3: Rules to define previous and/or concomitant medications

Start date of medication/procedure			Stopping rule (see Table 2)	Medication/ procedure
Day	Month	Year		
UNK	UNK	UNK	Before treatment start	Previous
UNK	UNK	UNK	After treatment start	Previous and concomitant
UNK	UNK	<= Treatment start (year)	Before treatment start	Previous
UNK	UNK	<= Treatment start (year)	After treatment start	Previous and concomitant
UNK	UNK	> Treatment start (year) and <= Treatment end + 30 days (year)	After treatment start	Concomitant

Start date of medication/procedure			Stopping rule (see Table 2)	Medication/ procedure		
Day	Month	Year				
UNK	<= Treatment start (month and year)		Before treatment start	Previous		
UNK	<= Treatment start (month and year)		After treatment start	Previous and concomitant		
UNK	> Treatment start (month and year) and <= Treatment end + 30 days (month and year)		After treatment start	Concomitant		
<= Treatment start (date)			Before treatment start	Previous		
<= Treatment start (date)			After treatment start	Previous and concomitant		
> Treatment start (date) and <= Treatment end + 30 days (date)			After treatment start	Concomitant		

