12.3 Concomitant Medications

Concomitant treatments are medications, other than trial medications, which are taken by subjects any time on- trial (on or after the first day of study treatment for each subject) or within 30 days for Arm A and 35 days for Arm B after last dose of trial treatment. Medications started after 30 (resp. 35) days will be presented and flagged in listings but will not be taken into account in summary tables.

Concomitant medications will be summarized from the “Concomitant medications” eCRF page. The ATC-2nd level and PT will be tabulated as given from the most recent available version of WHO-DD, Sept. 2016 or later. If multiple ATC can be assigned to a drug, all ATCs will be reported.

In case the date values will not allow to unequivocally allocate a medication to concomitant medication, the medication will be considered as concomitant medication (see section 9 for incomplete or missing dates).

Concomitant medications will also be listed. The listing will include: subject identification number, formulation, dose level and all corresponding collected data-fields on the corresponding eCRF page.

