15.2 Adverse Events

All TEAEs will be summarized, i.e. those events that are emergent during treatment having been absent pre-treatment, or worsen relative to the pre-treatment state and with onset dates occurring within the first dosing day of trial treatment until 30 days after the last dose of trial treatment. If an adverse event started before treatment start and improved during treatment (i.e. with the same PT directly following, but lower grade) it should not be counted as a TEAE. However, if an adverse event started either before or during the treatment period and worsened during the treatment period this should be reported as a TEAE.

Counting rules and observation periods for AEs during the treatment period (TEAEs):

- The treatment period is defined from the first dosing day of trial treatment until 30 days after the last dose of trial treatment or the clinical cut-off date.
- If an AE is reported for a given subject more than once during treatment, the worst severity and the worst relationship to trial treatment will be tabulated.
- Adverse events related to trial treatment are those events with relationship missing, unknown or related to at least one treatment (M3814, RT or Cisplatin).
- Adverse events related to M3814 are those events related to M3814, regardless to relationship with RT and/or Cisplatin

- Adverse events related to RT are those events related to RT, regardless to relationship with M3814 and/or Cisplatin
- Adverse events related to Cisplatin are those events related to M3814, regardless to relationship with M3814 and/or RT
- In case a subject has events with missing and non-missing grades, the maximum of the non-missing grades will be displayed.

For identification of AE treatment emergence, incomplete dates will be handled using the rules presented in section 9.

AEs will be coded according to the current MedDRA. The severity of AEs will be graded using National Cancer Institute - Common Terminology Criteria for Adverse Events (NCI-CTCAE) version 4.03 toxicity grades.

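### In Phase Ia Arm B the TEAE and on-treatment windows normally close before the 12-week DLT window, so a late-onset DLT can be missing from the TEAE tables and be classed as a late toxicity

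*SAP*

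**What the plan says.** **Safety windows.** SAP Section 15.2 defines the period for TEAEs: "The treatment period is defined from the first dosing day of trial treatment until 30 days after the last dose of trial treatment". SAP Section 9 uses the same limit for laboratory and other evaluations: "On-treatment evaluations for safety analyses will be evaluations performed on or after Treatment Day 1 until 30 days after the last dose". Trial treatment means M3814, RT or cisplatin, so the clock starts at the last of the three. Neither rule separates Arm A from Arm B.

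**What depends on them.** Under SAP 15.2.1, the AE frequency tables take only events with onset inside that period. Under SAP 15.2.3, an event that starts after it is late if it is a first occurrence of the preferred term, a recurrence after a gap, or a recurrence at a worse grade. Under SAP 15.4, the CTC shift tables use the worst on-treatment grade.

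**DLT window.** For Arm B, the Dose Escalation set in SAP 8.2 requires follow-up through "12 weeks [Phase Ia, Arm B] after start of M3814 treatment". Protocol 7.4.1.5 agrees and also counts from the start of the study drug: "12 weeks (Phase Ia, Arm B and Phase Ib, first 3 subjects in the expansion cohort of Arm A [NSCLC]) after the first dose of".

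**Concomitant medication.** SAP 12.3 uses a different limit: "within 30 days for Arm A and 35 days for Arm B after last dose of trial treatment". SAP 12.4 does the same for procedures. SAP Table 3, which classifies these records by date, allows 30 days after treatment end with no arm distinction.

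**The concern.** The primary endpoint and the secondary safety tables observe Arm B subjects for different lengths of time, and the DLT window is normally the longer one. No rule makes a DLT a TEAE, and none keeps a DLT out of the late-toxicity outputs. The SAP could therefore report one event as a DLT in the primary table, omit it from the Grade ≥3 related-event table for the same dose level, and list it as a late toxicity.

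That label conflicts with the protocol. Section 5.1 describes the DLT period as evaluating acute toxicity, and Section 3.6 places late RT toxicity at three months or more after RT. Here the label would attach about one month after RT.

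Cohorts have 3 subjects, so one omitted event matters to a dose level's table: 1/3 = 33 percentage points with one cohort at that dose, or 1/6 = 17 points with two pooled cohorts.

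**Working it through.** **Inputs**
- Arm B radiotherapy (protocol 5.1): "RT (2 Gy x 33 to 35, 5 F/W) is given with concurrent cisplatin administration".
- DLT window: 12 weeks = 84 days, with Day 1 the first M3814 dose. The introduction to SAP Section 15 counts from the start of RT instead, which is normally the same day.
- TEAE and on-treatment limit: last dose + 30 days.
- Permitted RT delay: up to 7 days in total (protocol 6.6.3.1).

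**The plan's own figure.** Protocol Table 5 sets the Arm B DLT evaluation period as the fraction days plus PTD 1 to 35. With 35 fractions at 5 per week: 35/5 = 7 weeks = 49 days, and 49 + 35 = 84 days = 12 weeks. The figure reproduces. Arm A also agrees: 14 + 21 = 35 days = 5 weeks.

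**Gap** = 84 − (day of last fraction + 30), with fractions on weekdays only, over all five starting weekdays:

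| Fractions | Last fraction | Windows close | Gap (days) |
|---|---|---|---|
| 33 | Day 45 or 47 | Day 75 or 77 | 9 or 7 |
| 34 | Day 46 or 48 | Day 76 or 78 | 8 or 6 |
| 35 | Day 47 or 49 | Day 77 or 79 | 7 or 5 |

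The range is 5-9 days, or 5/84 = 6% to 9/84 = 11% of the DLT window. With a Monday start it is 7-9.

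**Sensitivity**
- DLT window ending on Day 85: 6-10 days.
- Table 5 nominal count, PTD 35 against PTD 30: 5 days.
- RT delay, added as calendar days: 5 days of delay gives 0 to 4, and 7 days gives −2 to 2.
- A cisplatin dose after the last fraction would also shorten the gap.
- All treatment stopped early: 12-14 days after FD 30, 14-16 after FD 28, 40-42 after FD 10. FD 28 is 28/35 = 80% of planned RT. A subject who also received at least 80% of planned M3814 and completed the DLT period therefore stays in the Dose Escalation set. A subject with a DLT stays in whatever amount was received.
- Arm A: last fraction on Day 12-14, windows close on Day 42-44, after the 35-day DLT window. No gap.

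**Outputs affected**
- *AE tables.* A first-onset DLT in the gap fails the onset test in SAP 15.2.1 and meets the first-occurrence criterion in SAP 15.2.3.
- *Laboratory tables.* The PTD 35 visit has a ±2-day window (PTD 33-37), so a visit made in window always falls after PTD 30. Its values leave the CTC worst-grade shift tables. They stay in the normal-range shift tables, which use the worst on-trial value, and in the listings. Protocol 8.5.4.2 asks for the worst on-trial grades.

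**The case against.** **The 30-day limit is the protocol's own.** Protocol 7.4.1.3 ends TEAEs 30 days after RT, and 8.5.4.1 analyses them to the same limit. TEAE and DLT windows serve different purposes, and nothing requires them to end together. This stands: a reader should not infer that the SAP departed from the protocol. It explains where the mismatch comes from but does not reconcile the tables.

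**The event is not lost.** A reader might infer that a gap DLT goes unreported or that the report understates Arm B toxicity. The documents do not support that. SAP 15.1 gives a DLT table and a DLT listing. SAP 15.2.1 lists all AEs, emergent or not, with DLT and TEAE flags. SAP 15.2.3 tabulates late toxicities by grade. The omission is confined to the TEAE-based tables.

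**Dose escalation is unaffected.** SMC reviews follow completion of the DLT period in each cohort and are covered by a separate analysis plan (SAP Sections 4 and 6).

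**The exposed class is narrow.** Mucositis, stomatitis-associated toxicity and radiation dermatitis that become DLTs by lasting more than 4 weeks after treatment usually begin during RT, and those that do remain TEAEs. The problem needs a first onset, or a qualifying recurrence, more than 30 days after the last dose.

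**Extending the window has a cost.** Protocol 6.6.2 prohibits other anticancer therapy only up to 30 days after RT, so a longer window can admit events that start under subsequent treatment. Phase Ib Arm B would keep 30 days for the same regimen. Both points stand and shape the fix.

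**Conclusion.** The mismatch is real and limited to Phase Ia Arm B. It is 5-9 days for 33-35 fractions without interruption, less or nothing with permitted RT delay, and weeks after early stop of all treatment. The 5-9 days is not a fixed range and rests on weekday-only fractions, no delay and a DLT window ending on Day 84.

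The consequence is conditional. If a treatment-related DLT first starts in the gap, the TEAE, Grade ≥3 and related-event tables omit it and the late-toxicity outputs misclassify it. The PTD 35 laboratory values are excluded from the CTC on-treatment shift tables at every in-window visit, whether or not a DLT occurs. The primary DLT analysis, the listings and the dose decisions are sound.

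The correction is worth making because it is cheap and concerns how a primary-endpoint event is classified. The 30-day against 35-day conflict between SAP Table 3 and SAP 12.3 and 12.4 is a separate, minor inconsistency.

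**What to change.** **Preferred.** For Phase Ia Arm B, end the TEAE and on-treatment period at the later of last dose + 30 days and the end of the 12-week DLT period. Flag events that start after subsequent anticancer therapy. Borrowing the 35-day limit from SAP 12.3 would not be enough: 84 − (45 to 49) − 35 leaves 0-4 days.

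**Alternative.** Keep the protocol's 30-day TEAE definition. Add DLTs with onset in the DLT period to the Grade ≥3 and related-event tables with a footnote, and exclude them from late toxicities in SAP 15.2.3. This avoids a second TEAE definition but leaves the PTD 35 values outside the CTC shift tables.

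Record whichever is chosen in SAP Section 7.

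**Separately.** Align SAP Table 3 with the 35-day Arm B limit in SAP 12.3 and 12.4.

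**Cost.** A few lines of SAP text and an arm-specific end date in the programs. With the preferred option, the Phase Ia Arm B window differs from the protocol definition, from Arm A and from Phase Ib, and the tables should say so.

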2.0	20 March 2019	PPD	
- New template. Replace Statistical Analysis Plan (SAP) with Integrated Analysis Plan (IAP)- Update PPD [REDACTED] as coordinated author (replacing PPD [REDACTED])- Add PPD [REDACTED] (PPD [REDACTED] and PPD [REDACTED] [REDACTED] as data analysts- Updated PPD [REDACTED] as PPD Biostatistics Author (replacing P [REDACTED])- Updated PPD [REDACTED] senior reviewer from PPD [REDACTED]- Update protocol version with V9.0 (addition of Arm B: cisplatin exposure added, addition of some baseline characteristics: BSA, HPV, audiogram, adverse events outputs updated with Cisplatin)- CCI [REDACTED]- Update PK section- Update DLT period and treatment period definitions for Arm B- Add clarification for confirmed BOR derivation- Update concomitant procedures to flag procedures after treatment period- Add details for some listings- Update laboratory parameters section (put Phosphorus as gradable parameter, add clarifications about Uric acid grading)- Add clarifications for visits to display for ECG analysis- Update TEAE definition- Added categories for age so in line with BOA- Removal of time-windowing for on-treatment period- Added listing for late toxicities- Added clarification for use of unscheduled visits for Clinical laboratory data and vital signs- Alignment with Protocol v9.0 wording
3.0	18 August 2020	PPD [REDACTED]	
Update PK section to add analysis of CCI [REDACTED] CCI [REDACTED]Add table for disease history.Add analysis to assess COVID-19 impact on the study.

CONFIDENTIAL
INFORMATION

8/60

4**Purpose of the Integrated Analysis Plan**

The purpose of this IAP is to document technical and detailed specifications for all analyses of data collected for protocol EMR100036-002 for the Phase Ia (dose escalation part). Results of the analyses described in this IAP will be included in the Clinical Trial Report (CTR). Additionally, the planned analyses identified in this IAP will be included in regulatory submissions or future manuscripts. Any post-hoc, or unplanned analyses performed to provide results for inclusion in the CTR but not identified in this prospective IAP will be clearly identified in the CTR.

The IAP is based upon section 8 (Statistics) of the trial protocol and protocol amendments and is prepared in compliance with ICH E9.

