A separate IAP will document technical and detailed specifications for the analysis to provide to the SMC members prior to each SMC meeting for the dose escalation phase of Phase Ia.

Additionally, separated IAPs will be issued for the Phase Ib (expansion part) and the ancillary cPOP part of the trial.

5**Objectives and Endpoints**

	Objective	Endpoint	IAP section
Primary Objective	To determine the maximum tolerated dose (MTD) and recommended Phase II dose (RP2D) of M3814 in combination with RT (Arm A) and CRT (Arm B)	Primary Endpoint 
• DLT	15.1
Secondary Objective	To evaluate the safety profile and tolerability of M3814 in combination with RT (Arm A) and CRT (Arm B)	Secondary Endpoint 
• AE• Laboratory values• Vital signs• Macroscopic signs of bleeding• ECOG• ECG	15.2 15.4 15.5 15.6.1 15.6.2 15.6.3
	To explore the antitumor activity of M3814 in combination with RT (Arm A) and CRT (Arm B)	Secondary Endpoint 
• BOR• Tumor size measurements	14.1 14.1
	To assess the pharmacokinetics (PK) of M3814	
• Pharmacokinetic parameters of M3814	16.1

CCI

6 Overview of Planned Analyses

Statistical analyses will be performed using eCRF data obtained until clinical cut-off dates as described below.

In the Phase Ia, the Safety Monitoring Committee (SMC) will decide on DLTs relevant for the treatment and will decide by consensus on dose escalation, dose de-escalation, extension at same dose level, or suspension of enrollment based on safety and PK data.

The cut-off date for dose escalation assessments will be triggered by the completion of the DLT period of the last subject in the respective cohort. For each SMC meeting, a data snapshot will be taken from the clinical database. A dedicated IAP provides more details for the analysis to be sent to SMC members prior to each SMC meeting.

This IAP covers the analyses for efficacy and safety of two milestones:

- Secondary safety analysis
- Final analysis

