15.2.1 All Adverse Events

Population: SAF analysis set

Adverse events will be summarized by worst severity (according to NCI-CTCAE version 4.03) per subject, using the most recent available MedDRA version (19.1 or later) PT as event category and primary SOC body term as Body System category.

Frequency tables for AEs captured on the “Adverse Events” eCRF pages will be based on TEAEs, i.e. those events with onset dates occurring within the treatment periods (as defined above).

A first overview table of adverse events will be provided by dose level and overall by summarizing the number and percentage of patients with any:

- TEAE
- TEAEs related to trial treatment, (i.e. M3814, RT, or Cisplatin)
- TEAEs related to M3814
- TEAEs related to RT
- TEAEs related to Cisplatin
- Serious TEAE
- Serious TEAE related to trial treatment, M3814, RT or Cisplatin
- TEAEs with grade ≥ 3
- TEAEs with grade ≥ 4
- TEAEs with grade ≥ 3 related to trial treatment, M3814, RT or Cisplatin
- TEAEs with grade ≥ 4 related to trial treatment, M3814, RT or Cisplatin

- TEAE leading to study discontinuation
- TEAE leading to death
- TEAE leading to death related to trial treatment, M3814, RT or Cisplatin

In addition, frequency tables summarizing events in the following categories will be prepared by dose level and overall, SOC and PT in alphabetical order:

- TEAEs
- TEAEs related to trial treatment (i.e., M3814, RT, or Cisplatin)
- TEAEs related to M3814
- TEAEs related to RT
- TEAEs related to Cisplatin
- Serious TEAEs
- Serious TEAEs related to trial treatment
- Serious TEAEs related to M3814
- Serious TEAEs related to RT
- Serious TEAEs related to Cisplatin
- TEAEs by worst CTCAE grade: any grade (including AEs with missing grade), grades ≥ 3 , ≥ 4 and 5
- TEAEs related to trial treatment by worst CTCAE grades: any grade (including AEs with missing grade), grades ≥ 3 , ≥ 4 and 5
- TEAEs related to M3814 by worst CTCAE grades: any grade (including AEs with missing grade), grades ≥ 3 , ≥ 4 and 5
- TEAEs related to RT by worst CTCAE grades: any grade (including AEs with missing grade), grades ≥ 3 , ≥ 4 and 5
- TEAE related to Cisplatin by worst CTCAE grades: any grade (including AEs with missing grade), grades ≥ 3 , ≥ 4 and 5
- TEAEs leading to death
- TEAEs related to trial treatment leading to death
- TEAEs related to M3814 leading to death
- TEAEs related to RT leading to death
- TEAEs related to Cisplatin leading to death

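### SAP 15.2 defines cisplatin-related adverse events by relationship to M3814, so as written the Arm B cisplatin tables would duplicate the M3814 tables

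*SAP*

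**What the plan says.** SAP 15.2 (Adverse Events) sets out four relatedness rules under its counting rules.

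- Any trial treatment: "Adverse events related to trial treatment are those events with relationship missing, unknown or related to at least one treatment", with M3814, RT and cisplatin then listed in brackets.
- M3814: "Adverse events related to M3814 are those events related to M3814, regardless to relationship with RT and/or Cisplatin".
- RT: "Adverse events related to RT are those events related to RT, regardless to relationship with M3814 and/or Cisplatin".
- Cisplatin: "Adverse events related to Cisplatin are those events related to M3814, regardless to relationship with M3814 and/or RT".

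SAP 15.2.1 then plans cisplatin-related outputs next to the M3814 and RT ones. There are overview rows, some written as combined lines such as "Serious TEAE related to trial treatment, M3814, RT or Cisplatin", and separate frequency tables by system organ class and preferred term. The adverse event listing carries one relatedness flag per treatment.

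The modification history (SAP Section 3), cited here only for intent, records for version 2.0 "adverse events outputs updated with Cisplatin". SAP Section 5 makes adverse events a secondary endpoint for M3814 with chemoradiotherapy in Arm B. Protocol 8.5.4.1 asks for events to be reported separately by relationship to M3814, RT, CRT or their combination.

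**The concern.** The cisplatin rule uses M3814 as its criterion and, in the same sentence, lists M3814 among the relationships to disregard. It contradicts itself and breaks the pattern of the two rules above it. Neither document defines cisplatin-relatedness anywhere else, so nothing overrides it.

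The SAP has no CRT-related category. The cisplatin outputs are therefore its only adverse event summaries that attribute events to the chemotherapy component. Under the literal rule they would carry no information about cisplatin.

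The omitted events are not hypothetical in kind. Table 14 of the protocol describes cisplatin nephrotoxicity, ototoxicity and neurotoxicity, and an investigator could well attribute such events to cisplatin and not to M3814. The documents give no frequency for this.

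**Working it through.** The plan states no figure to reproduce. The check is a comparison of classification rules, followed by a count of the outputs that use them.

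**1. Apply the rules to every attribution pattern.** With yes/no attribution to M3814, RT and cisplatin there are 2 × 2 × 2 = 8 patterns. RT does not enter any of the three rules compared here, so each row below stands for two patterns (RT yes and RT no).

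| Related to M3814 | Related to cisplatin | M3814 rule | Cisplatin rule as written | Cisplatin rule on the pattern of the other two |
|---|---|---|---|---|
| no | no | no | no | no |
| no | yes | no | **no** | yes |
| yes | no | yes | **yes** | no |
| yes | yes | yes | yes | yes |

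- The written cisplatin rule agrees with the M3814 rule in all 4 rows (8 of 8 patterns).
- Against the evident intent it is wrong in 2 of 4 rows (4 of 8 patterns): 2 patterns omitted and 2 wrongly included.

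These are counts of patterns, not of events. Omissions and wrong inclusions can partly cancel in subject totals.

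**2. Count the Arm B outputs that use the rule.** SAP Section 9 produces outputs by arm, and protocol 6.2 gives cisplatin in Arm B only.

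- Frequency tables (SAP 15.2.1): related; serious related; related by worst grade; related leading to death = 4.
- Overview table (SAP 15.2.1): related; serious; grade 3 or higher; grade 4 or higher; fatal = 5 rows in 1 table. The first row is explicit. The other four come from reading each combined line as one row per attribution.
- Listings with the cisplatin flag: all adverse events, and the COVID-19 listing, which takes the same items = 2.

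Total: 4 + 1 + 2 = 7 outputs, or 8 if the serious adverse event listing takes its items from 15.2.1, as SAP 15.3.2 suggests. The listings count only if the flag is derived from the rule.

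**3. Outputs that do not use the rule.**

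- The DLT summary (SAP 15.1): protocol 7.4.1.5 asks only for a relationship to any study treatment.
- The pooled trial-treatment tables, whose rule names cisplatin correctly.
- The discontinuation tables (SAP 15.2.2), which go by action taken.
- The late-toxicity outputs (SAP 15.2.3), which include no cisplatin listing.

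**4. Weight of one subject.** The tables use the safety set, whose Arm B size is not stated. The protocol synopsis anticipates 30 participants in Arm B escalation and a 10% drop-out for DLT evaluability.

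- Assuming 30 subjects: 1/30 = 3.3 percentage points per net misclassified subject in the overall column.
- Assuming 30/0.9 = 33.3, about 33 subjects: 1/33 = 3.0 points.
- In a dose-level column holding a single cohort of 3: 1/3 = 33.3 points.

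These are weights per subject, not expected effects.

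**The case against.** The strongest reply is that nobody would follow the rule literally. It defeats itself, the two neighbouring rules show the pattern, the pooled rule lists the three treatments separately, and planning M3814 and cisplatin tables side by side would be pointless if they were identical by definition. The stakes are also limited. The primary endpoint is untouched, the protocol names CRT rather than cisplatin alone as a category, cisplatin is standard-of-care treatment given alongside the only investigational product, and SAP 15.2.2 separately tabulates events leading to cisplatin interruption or withdrawal.

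Most of this stands as a limit on weight. The intended meaning can be inferred, and harm requires someone to code the text as it is. It does not make the rule correct. A program verified against this wording would pass with wrong tables, and a program that followed the intent would depart from the plan. The discontinuation tables record action taken, not causality, so they do not replace the cisplatin-related tables.

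Two narrower objections are fair. The listings may show attribution as collected, in which case the firm core is the four frequency tables and at least one overview row. The pattern count says little more than that two yes/no flags can differ.

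**Conclusion.** The concern holds. The cisplatin rule in SAP 15.2 is wrong as written. Followed literally, it makes the four Arm B cisplatin frequency tables and the cisplatin overview rows identical to their M3814 counterparts, along with the listing flag if that flag is derived. This is a definite error in a counting rule for a secondary safety endpoint. It should be corrected, but it does not reach the primary endpoint or the pooled tables.

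The conclusion about identical outputs rests on the wording alone and needs no data. The practical effect depends on two things the documents do not give: how the rule was programmed, and how often attribution to M3814 and to cisplatin differ.

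**What to change.** In the cisplatin bullet of SAP 15.2, replace M3814 with cisplatin as the criterion, so that the rule selects events related to cisplatin whatever their relationship to M3814 or RT. Then check that the filters behind the cisplatin tables, overview rows and any derived flag use the cisplatin attribution field. The cost is one word and a program check.

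An optional clarification can be made at the same time. Protocol 8.5.4.1 treats a missing classification as related to the trial drug, while the SAP states a missing-relationship convention only in the pooled rule. The SAP also says "The IAP is based upon section 8 (Statistics) of the trial protocol and protocol amendments", so the convention can be read as carrying over to M3814, and no departure is shown. A clause in the M3814 bullet would settle it. It should cover both missing and unknown relationships, because the pooled rule names both. The effect depends on the number of such records, which is not given and is probably small.
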